### 7.2.2 BUN and Potassium:

**Sample Collection:** Samples for BUN and potassium will be collected pre- and post-dialysis on Days -7, -5, -3, 1, 3, 5, and 12.

**Change in BUN and Potassium values:** The change in BUN values on Days -7, -5, -3, 1, 3, 5, and 12 will be calculated by subtracting the post-dialysis BUN from the pre-dialysis BUN values for each day separately. The same method will be used for potassium.

Potassium and BUN values will be listed and summarized by treatment and Day in Tables and Figures for all subjects in the Safety Population (2 active dose levels and pooled placebo).

The level of precision for potassium and BUN summary statistic will be the same as per aPTT values listed in Section 7.2.1.

### 7.2.3 URR and KT/V

The derived PD parameters (URR and KT/V) will be calculated from the pre- and post-dialysis BUN values on Days -7, -5, 1, 3, 5, and 12.

URR will be calculated using the following formula:

$$\text{URR} = (1 - (\text{post-dialysis BUN} / \text{pre-dialysis BUN})) * 100$$

Kt/V will be calculated using the following formula:

$$sp \frac{Kt}{V} = \ln(R - (0.008 \times t)) + (4 - (3.5 \times R)) \times \frac{UF}{Wt}$$

Where R = BUN Post-dialysis/BUN Pre-dialysis  
t = Time of HD  
UF = Pre-dialysis Weight – Post-dialysis Weight  
Wt = Post-dialysis weight of patient.

URR and Kt/V values will be listed and summarized by treatment and Day in Tables for all subjects in the Safety Population (2 active dose levels and pooled placebo).

The level of precision for URR and Kt/V summary statistic will be the same as per aPTT values listed in Section 7.2.1

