11 STUDY POPULATION

11.1 Inclusion Criteria

Patients must fulfill all of the following inclusion criteria to be eligible for participation in the study:

1. ESRD maintained on stable outpatient HD regimen, using an established (> 3 months) and normally functioning, regular flow, uninfected first mature AV fistula (or AV graft) and skin consistent with standard chronic HD access injuries, and HD stability defined as $Kt/V \geq 1.2$ within 3 months prior to screening at a healthcare center for > 3 months from screening.
2. On HD regimen at least 3 times per week for a minimum of 3 hours per dialysis session, using a complication-free well maintained AV fistula (or AV graft), expected and plan to continue this throughout and for at least 3 months beyond the study.
3. Is capable of understanding the written informed consent, provides signed and witnessed written informed consent, and agrees to comply with protocol requirements and study-related procedures.
4. Willing to be confined to the CRU for the duration of the study, able to comply with all study-related requirements, and able to adhere to study restrictions and visit schedules.
5. Male or female, between 18 and 80 years of age (inclusive) at the time of screening.
6. BMI of ≥ 18 at the time of screening.
7. Considered by the PI to be clinically stable with respect to underlying ESRD, based on medical evaluation that includes medical and surgical history, and a complete physical examination including vital signs, ECG, and clinical laboratory test results at screening. Repeat assessments are permitted for any laboratory, ECG, or vital sign parameter required for enrollment.
8. Female patients must be of non-childbearing potential and must have undergone one of the following:
 - sterilization procedures at least 6 months prior to dosing;
 - hysteroscopic sterilization;
 - bilateral tubal ligation or bilateral salpingectomy;
 - hysterectomy;
 - bilateral oophorectomy;or be postmenopausal with amenorrhea for at least 1 year prior to dosing and follicle-stimulating hormone (FSH) serum levels consistent with postmenopausal status as per PI or designee judgment.

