13.3 Hemodialysis Procedure and Blood Clots in the Dialyzer Cartridge

Patients will undergo hemodialysis 3 times a week as delineated in the Study Events Flow Chart ([Section 6](#)). For each patient, the hemodialysis will last at least 3 hours as per patient standard schedule which will be the same throughout the study.

Patients undergoing heparin-free hemodialysis may be at higher risk of developing clots within the hemodialysis circuit. In order to monitor clotting within the HD circuit, venous pressure will be continuously monitored. Should clotting within the dialyzer occur, site standard operating procedures will be followed to replace the clotted dialyzer and resume hemodialysis under the supervision of the PI, if appropriate. It is important to note that replacement of the dialyzer cartridge is a safe procedure for the patient. While studies

suggest that there is no risk of thromboembolic complications should this occur, clotting of the dialyzer circuit could result in up to ~228 mL of blood loss.

The hemoglobin levels will be followed more closely.

If the patient clots the hemodialyzer twice they may be discontinued from the study at the discretion of the PI. If the patient fully clots the hemodialyzer, the continuation of the patient in the study will be at the PIs discretion.

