#### **7.1.2 Efficiency of HD**

Efficiency of HD will be assessed by:

- Blood BUN and potassium levels before and after dialysis;
- Length of HD – will be calculated as end time minus start time in hours and presented in individual and mean tables for each treatment;

- Total dialysate urea (measurement of BUN removed over 4 hours of dialysis) will be used to calculate;
  - Single pool Kt/V. The formula to calculate Kt/V is listed under Section 7.2.3.
  - URR measured as the difference between urea pre-dialysis and post-dialysis expressed as a percentage. The formula to calculate URR is listed under Section 7.2.3.

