**Notes for Generating the Actual Table:**

- n will be presented as an integer (with no decimal);
- Summary statistics will be presented with same precision as defined in post-text shells
- Internal template ITPar1, with the following changes: n will be presented in the column title with additional columns to be created.

For Table 12-2 through 12-5 the source tables will be 14.3.5.5

Program: /CAXXXXX/sas\_prg/pksas/intext-pk-tables.sas DDMMYYYY HH:MM  
 Program: /CAXXXXX/sas\_prg/pksas/adam\_intext\_pkparam.sas DDMMYYYY HH:MM

Table 11-5 Summary of Kt/V Values (Safety Population)

Time Point	Single pool Kt/V														
	Treatments														
	Single IV Infusion of 0.25 mg/kg xisomab 3G3					Single IV Infusion of 0.5 mg/kg xisomab 3G3					Placebo (Pooled)				
	R (unit) [n=xx]	t (unit) [n=xx]	UF (unit) [n=xx]	Wt (unit) [n=xx]	Kt/V (unit) [n=xx]	R (unit) [n=xx]	t (unit) [n=xx]	UF (unit) [n=xx]	Wt (unit) [n=xx]	Kt/V (unit) [n=xx]	R (unit) [n=xx]	t (unit) [n=xx]	UF (unit) [n=xx]	Wt (unit) [n=xx]	Kt/V (unit) [n=xx]
Day -7	XX.X	XX.X	XX.X	XX.X	XX.X	XX.X	XX.X	XX.X	XX.X	XX.X	XX.X	XX.X	XX.X	XX.X	XX.X
Day -5	XX.X	XX.X	XX.X	XX.X a	XX.X	XX.X	XX.X	XX.X	XX.X	XX.X	XX.X	XX.X	XX.X	XX.X	XX.X
Day -3	XX.X	XX.X	XX.X	XX.X	XX.X	XX.X	XX.X	XX.X	XX.X	XX.X	XX.X	XX.X	XX.X	XX.X	XX.X
Day 1*	XX.X	XX.X	XX.X	XX.X	XX.X	XX.X	XX.X	XX.X	XX.X	XX.X	XX.X	XX.X	XX.X	XX.X	XX.X
Day 3	XX.X	XX.X	XX.X	XX.X	XX.X	XX.X	XX.X	XX.X	XX.X	XX.X	XX.X	XX.X	XX.X	XX.X	XX.X
Day 5	XX.X	XX.X	XX.X	XX.X	XX.X	XX.X	XX.X	XX.X	XX.X	XX.X	XX.X	XX.X	XX.X	XX.X	XX.X
Day 12	XX.X	XX.X	XX.X	XX.X	XX.X	XX.X	XX.X	XX.X	XX.X	XX.X	XX.X	XX.X	XX.X	XX.X	XX.X

a-n=xx  
 \* - Single IV infusion of 0.25, 0.5 mg/kg xisomab 3G3 or placebo was administered on Day 1  
 Values will be presented as arithmetic mean

R= post-dialysis BUN/pre-dialysis BUN)\*100  
 t = Time of HD  
 UF = Pre-dialysis Weight – Post-dialysis Weight  
 Wt = Post-dialysis weight of patient  

$$Kt/V = \ln(R - (0.008 \times t)) + (4 - (3.5 \times R)) \times \frac{UF}{Wt}$$

Source: Tables 14.2.4.1.1 through 14.2.4.1.3  
 Program: /CAXXXX/sas prg/stsas/intext/t ac.sas DDMMYYYY HH:MM

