**Programmer Notes:**

Values will be reported at pre- and post-dialysis on Days -7, -5, -3, 1, 3, 5, 6, and 12.

The screening values to be reported if not presented in other tables.

Aronora, Inc.  
xisomab 3G3, Protocol 3G3-18-02  
Celerion, Clinical Study Report No. CA23900

---

For Tables 14.2.4.1.1 through 14.2.4.1.3, Kt/V will be reported on Days -7, -5, -3, 1, 3, 5, and 12. Column titles will be the same as per Table 11-5 shell (ie., R, t, UF, Wt, and Kt/V) with the following footnotes:

- Single IV infusion of 0.25, 0.5 mg/kg xisomab 3G3 or placebo was administered on Day 1
- $R = \text{post-dialysis BUN/pre-dialysis BUN}) * 100$
- t = Time of HD
- $UF = \text{Pre-dialysis Weight} - \text{Post-dialysis Weight}$
- Wt = Post-dialysis weight of patient
- $Kt/V = \ln(R - (0.008 \times t)) + (4 - (3.5 \times R)) \times \frac{UF}{Wt}$

For the bleeding time table in Section 14.3, values will be reported post-dialysis on Days screening (if available), -7, -5, -3, 1, 3, 5, 8, 10 and 12. There will be only one column underneath each dose as per Table 11-4 shell with the following footnote:

- Single IV infusion of 0.25, 0.5 mg/kg xisomab 3G3 or placebo was administered on Day 1

Program: /CAXXXX/sas\_prg/pksas/xxxxxxxx.sas DDMMYYYY HH:MM  
Program: /CAXXXX/sas\_prg/pksas/xxxxxxxx.sas DDMMYYYY HH:MM

Aronora, Inc.  
 xisomab 3G3, Protocol 3G3-18-02  
 Celerion, Clinical Study Report No. CA23900

---

Tables 14.2.6.1 will be in the following format:

Table 14.2.6.1 Summary of Clotting in the Drip Chamber - Days -7 to 12 (Safety Population)

Day	Time Point	0.25 mg/kg Xisomab 3G3					0.5 mg/kg Xisomab 3G3					Pooled Placebo				
		Category*					Category*					Category*				
		1	2	3a	3b	4	1	2	3a	3b	4	1	2	3a	3b	4
Day -7	2 hr after HD	X	X	X	X	X	X	X	X	X	X	X	X	X	X	X
	Post HD	X	X	X	X	X	X	X	X	X	X	X	X	X	X	X
Day X	2 hr after HD	X	X	X	X	X	X	X	X	X	X	X	X	X	X	X
	Post HD	X	X	X	X	X	X	X	X	X	X	X	X	X	X	X

<include all days and timepoints>

Note: \*Category:1=No detectable clotting, 2=Presence of fibrinous ring or minimum clot affecting less than 5% of chamber space,  
 3a=Clot formation (affecting more than 5% of but less than 30% of chamber space) but dialysis still possible,  
 3b=Clot formation (affecting more than 30% of chamber space) but dialysis still possible,  
 4=Complete occlusion of chamber  
 HD: hemodialysis

Program: /AAXXXX/ECR/sas\_prg/stsas/tab\_PROGRAMNAME.sas DDMMYYYY HH:MM

Aronora, Inc.  
 xisomab 3G3, Protocol 3G3-18-02  

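### The SAP's Kt/V formula has no minus sign on the logarithm and its table shells define R as a percentage, so Kt/V computed as specified is negative or meaningless

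*SAP*

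**What the plan says.** SAP section 7.2.3 gives single-pool Kt/V as "\ln(R - (0.008 \times t)) + (4 - (3.5 \times R)) \times \frac{UF}{Wt"}, with the legend "Where R = BUN Post-dialysis/BUN Pre-dialysis". UF is the weight lost over the session and Wt is the post-dialysis weight. The legend gives no unit for t.

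The formula is printed twice more. The Table 11-5 shell (SAP 11.1) has "Kt/V = \ln(R - (0.008 \times t)) + (4 - (3.5 \times R)) \times \frac{UF}{Wt"}, and the programmer notes for Tables 14.2.4.1.1 to 14.2.4.1.3 (SAP 11.3) carry the same expression. Neither has a minus sign before the logarithm. Both define R differently from section 7.2.3: "R= post-dialysis BUN/pre-dialysis BUN)\*100" in the first and "R = \text{post-dialysis BUN/pre-dialysis BUN}) * 100" in the second, each with an unbalanced bracket.

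Protocol 13.5 and SAP 2.2 describe Kt/V as dialyzer clearance times time over body water. Protocol 11.1, criterion 1, has "HD stability defined as $Kt/V \geq 1.2". Protocol 9.2 lists Kt/V and URR as secondary measures of efficacy on hemodialysis efficiency. SAP section 9, which records departures from the protocol, says nothing about the formula.

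**The concern.** There are two separate errors. The sign of the logarithm contradicts the documents' own definition of Kt/V, a ratio of positive quantities. The scale of R contradicts itself between the SAP text and the shells.

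The shells and programmer notes are what the table programs are written from, so a program that follows them reproduces the error. Under the section 7.2.3 version, an effect of the drug on urea clearance would be reported in the wrong direction. Under the shell version, Kt/V would mostly reflect how much fluid was removed. Some of those values would look plausible, which makes the error harder to notice.

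**Working it through.** **Inputs.** The formula and both definitions of R are as above. Length of dialysis "will be calculated as end time minus start time in hours" (SAP 7.1.2), so t is taken in hours. For its value, Protocol 13.3 says "For each patient, the hemodialysis will last at least 3 hours as per patient standard schedule" and SAP section 9 says about 4 hours. The documents give no BUN ratios or fluid losses. R and UF/Wt are therefore assumptions, and ranges are shown.

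**Which sign is right.** With no weight change and no urea generation, clearance K from volume V gives R = exp(-Kt/V), so Kt/V = -ln(R). The leading term must carry a minus sign.

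**The plan's own figure.** The plan prints no worked Kt/V value; its only number is the 1.2 threshold. With -ln, R as a fraction and t = 4 h, the formula returns 1.2 at R = 0.333 (UF/Wt = 0) to R = 0.376 (UF/Wt = 0.05). As printed in section 7.2.3, those sessions return -1.20 to -0.93.

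**One session: R = 0.30, t = 4 h, UF/Wt = 0.03.**
- Section 7.2.3: ln(0.30 - 0.032) + (4 - 1.05) x 0.03 = -1.317 + 0.089 = -1.228.
- With -ln: 1.317 + 0.089 = 1.405 (unrounded terms).
- Shells, R = 30: ln(30 - 0.032) + (4 - 105) x 0.03 = 3.400 - 3.030 = 0.370.

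**Varying fluid removal, R = 0.30, t = 4 h.**

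| UF/Wt | 7.2.3 as printed | Shells (R x 100) | Sign corrected only, R x 100 | Both corrected |
|---|---|---|---|---|
| 0 | -1.317 | 3.40 | -3.40 | 1.317 |
| 0.02 | -1.258 | 1.38 | -5.42 | 1.376 |
| 0.03 | -1.228 | 0.37 | -6.43 | 1.405 |
| 0.04 | -1.199 | -0.64 | -7.44 | 1.435 |
| 0.05 | -1.169 | -1.65 | -8.45 | 1.464 |

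At fixed R, the both-corrected value moves by 0.15 across this range; the shell version moves by 5.05. Correcting the sign alone does not rescue the shells.

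**Wider range.** For R = 0.10 to 0.70 and UF/Wt = 0 to 0.06 (793 grid points per duration), the section 7.2.3 version is negative at every point: -2.58 to -0.30 at 3 h and -2.69 to -0.31 at 4 h. At R = 0.30, UF/Wt would have to be about 0.44 to reach zero. The shell version runs from -10.2 to 4.25; 416 of 793 points are positive and 148 of 793 fall between 0.8 and 2.0.

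**Direction.** At t = 4 h and UF/Wt = 0.03, improving R from 0.35 to 0.25 moves the section 7.2.3 result from -1.06 to -1.43, while the correct value rises from 1.23 to 1.62. In the shell version the order reverses only when UF/Wt is below 1/[3.5 x (100R - 0.008t)]. At 4 h that is about 0.014, 0.010 and 0.007 for R = 0.20, 0.30 and 0.40.

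**Dropping the sign afterwards.** The absolute value subtracts the fluid term instead of adding it. At t = 4 h, R = 0.20 and UF/Wt = 0.02 it gives 1.718 against 1.850 (7% low). At R = 0.40 and UF/Wt = 0.05 it gives 0.870 against 1.130 (23% low).

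**Unit of t.** If t were entered in minutes, 0.008 x 240 = 1.92 exceeds any R below 1 and the logarithm is undefined.

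**The case against.** The equation is typeset, and a leading minus could be lost when the PDF is converted to text. The three printings look like one pasted equation, so they are not fully independent. This cannot be excluded, but it is unlikely: the other minus signs in the same expression survived in all three places. The conflict over R does not depend on it.

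The 1.2 entry value is a pre-study criterion, and nothing says it was computed with this formula. That is fair. It shows the scale the documents expect, not that every session must reach 1.2; the positive definition of Kt/V carries the argument.

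The SAP says its shells may change, and R, t, UF and Wt are tabulated beside Kt/V, so a wrong value could be noticed and recalculated. Kt/V is summarized descriptively, no decision rule uses it, the sample size was chosen without statistical considerations, and URR comes from the same BUN pair with a correct formula. All this stands and limits the damage. It does not make the specification right, and values such as 1.38 from the shell version would not draw attention.

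**Conclusion.** The concern holds. As specified in section 7.2.3, Kt/V is negative for every session in the range examined and falls as clearance improves. As specified in the shells, it varies in sign and depends mainly on fluid removal. The typical error is large: -1.23 or 0.37 where 1.41 is correct.

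The exact sizes rest on assumed R and UF/Wt. The sign does not, within any realistic session: extending R to 1 (no urea removed), with t = 3 to 5 h and UF/Wt up to 0.06, the section 7.2.3 formula reaches at most ln(0.976) + 0.5 x 0.06 = 0.006. The consequence also assumes that the program follows the SAP. It is confined to one descriptive secondary endpoint, but for that endpoint the specification is wrong as written and must be corrected.

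**What to change.** In section 7.2.3, the Table 11-5 shell and the notes for Tables 14.2.4.1.1 to 14.2.4.1.3, write:

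spKt/V = -ln(R - 0.008 x t) + (4 - 3.5 x R) x UF/Wt

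- Define R as post-dialysis BUN divided by pre-dialysis BUN, as a fraction, in all three places, and delete the factor of 100.
- State in each legend that t is in hours and that UF and Wt are both in kg. Section 7.1.2 and the weight measurements already imply this.
- Add a programming check that flags any non-positive Kt/V, and a test case: R = 0.30, t = 4 h, UF/Wt = 0.03 must return 1.405.
- In the same edit, reconcile the days: section 7.2.3 omits Day -3 for URR and Kt/V, while the Table 11-3 and Table 11-5 shells include it.

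The cost is SAP and shell wording only. BUN, dialysis times and weights are already collected, so no data, sample or visit changes. If tables have already been programmed, Kt/V has to be rerun from the same inputs.

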9.2 Endpoints

Primary outcome measures:

- The safety and tolerability of xisomab 3G3 will be evaluated versus pre-treatment and placebo by reviewing number and severity of adverse events and use of concomitant medications, physical examination, vascular access site reaction, bleeding time, and changes in vital signs, ECGs, and clinical laboratory evaluations.

Secondary outcome measures:

- PD using dose-dependency of drug potency, determined by measuring changes in coagulation parameters, and thrombus accumulation (assessed and ranked by visual inspection) within the dialyzer cartridges and total protein accumulation in the HD filter after xisomab 3G3-treatment versus pre-treatment and placebo.
- Efficacy on hemodialysis efficiency using BUN and potassium levels before and after hemodialysis, length of HD, measurement of urea removed by 3 hours of dialysis, and total dialysate urea (single pool Kt/V and URR) after xisomab 3G3-treatment versus pre-treatment and placebo.

Other outcome measures:

- PK parameters of xisomab 3G3, calculated, as appropriate: AUC0-t, AUC0-inf, AUC%extrap, Cmax, Tmax, Kel, t^{1/2}, CL, and Vss.
- Development of immunity or antibodies against xisomab 3G3 after drug exposure.

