14.1 Sample Size Determination

The sample size chosen for this study was selected without statistical considerations. The sample size of up to 24 patients in total (9-12 per cohort with a ratio of 2:1 of active study drug:placebo) has been determined adequate to meet the study safety, tolerability, PD, and PK objectives.

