14.3.1 Safety and Tolerability Analyses

All safety data will be populated in the individual CRFs. All safety data will be listed by patients.

The placebo patients from all cohorts will be pooled into a single placebo group for all summaries and presentations

Dosing dates and times will be listed by patient.

Incidence and time of bleeding from the HD access sites on the AV fistula (or AV graft), as described in [Section 13.2.6](#), will be counted and recorded. Treatment versus pre-treatment, placebo, and post-treatment results will be compared.

AEs will be coded using the most current version of Medical Dictionary for Regulatory Activities (MedDRA®) available at Celerion and summarized by treatment (2 active dose levels and pooled placebo) for the number of patients reporting the treatment emergent adverse event (TEAE) and the number of TEAEs reported. A by-patient AE data listing including verbatim term, coded term, treatment, severity, and relationship to study drug will be provided.

Safety data including ECGs, vital signs assessments, clinical laboratory results and vascular access site reaction, will be summarized by treatment (2 active dose levels and pooled placebo) and point of time of collection.

Descriptive statistics using appropriate summary statistics will be calculated for quantitative safety data as well as for the difference to baseline, when appropriate. In addition, a shift table describing out of normal range shifts will be provided for clinical laboratory results.

Concomitant medications will be listed by patient and treatment (2 active dose levels and pooled placebo) and coded using the most current version of WHO drug dictionary available at Celerion. Medical history will be listed by patient.

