14.3.3 Pharmacodynamic Analyses

Placebo patients from Cohort 1 and Cohort 2 will be pooled for analysis.

The PD analysis will include assessments of drug potency and efficiency of HD. These will include change in aPTT, BUN, and potassium levels. Change in thrombus accumulation, in total dialysate urea, URR, and Kt/V after xisomab 3G3 levels versus pre-treatment and placebo will also be evaluated. Total protein accumulation within HD filter will be evaluated.

The change from baseline in PD endpoints will be summarized by treatment (2 active dose levels and pooled placebo) and at each scheduled time point using descriptive statistics. The baseline values are any value observed from Day -7 to Day 1, prior to xisomab 3G3 administration. Any values after a single dose of xisomab 3G3 are regarded as post baseline values.

The change from baseline variables will be calculated as the post-baseline value minus the value at baseline.

Additional analyses may be performed as deemed necessary upon review of the data.

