## 1. INTRODUCTION

The following statistical analysis plan (SAP) provides the framework for the summarization of the data from this study. The SAP may change due to unforeseen circumstances. Any changes made from the planned analysis within the protocol, after the unblinding, or locking of the database will be documented in the clinical study report (CSR). The section referred to as Table Shells within this SAP describes the traceability of the tables, figures, and listings (TFLs) back to the data. Note that the header for this page will be the one used for the main body of the CSR.

Any additional exploratory analyses not addressed within this statistical analysis plan (SAP) and/or driven by the data, or requested by Aronora Inc., will be considered out of scope and must be described in the CSR.

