## 7.2 Data Summarization and Presentation of PD Parameters

### 7.2.1 aPTT

**Sample Collection:** Samples for the coagulation parameter (aPTT) will be collected at screening, pre- and post-dialysis on Days -7, -5, -3, 1, 3, 5, and 12. Additional samples for aPTT will be collected following xisomab 3G3/placebo dosing on Day 1 at predose (hour 0, at least 1 hour prior the start of HD session) and at 0.167, 0.5, 1, 2, 3, 4, 6, 8, 12, 16, 24, 48, 96, 120, 144, and 192, hours after xisomab 3G3 start of infusion.

**Baseline Calculation Method Following Day 1 Dosing:** Following xisomab 3G3 dosing on Day 1, aPTT change from baseline will be calculated by dividing postdose aPTT values from average of pre-dose baseline (the average of pre-dialysis aPTT values on Days -7, -5, -3, and 1 will be calculated as pre-dose baseline).

**Fold change in aPTT values:** The fold change in aPTT values on Days -7, -5, -3, 1 (only pre- and post-dialysis aPTT values on Day 1), 3, 5, and 12 will be calculated by dividing the post-dialysis aPTT/pre-dialysis aPTT values for each day separately.

aPTT values will be extracted from the clinical laboratory database and descriptive statistics will be generated using SAS® version 9.3 or higher. Following Day 1 xisomab 3G3 dosing, a table will be presented for the aPTT change from baseline with descriptive statistics.

aPTT values will be listed and summarized by treatment and time points in Tables and Figures for all subjects in the Safety Population (2 active dose levels and pooled placebo). aPTT values will be presented with the same level of precision as received from the clinical laboratory database. Summary statistics, including n, Mean, SD, CV%, SEM, minimum, median, and maximum will be calculated for all nominal values time points. Excluded subjects will be included in the aPPT values tables, but will be excluded from the summary statistics and noted as such in the tables.

Mean and individual aPTT values-time and change from baseline-time profiles will be presented on linear scale. Linear mean plots will be presented with and without SD.

The level of precision for the aPPT values summary statistic will be presented as follows:

- minimum/maximum: in same precision as in the clinical laboratory database
- Mean/median: in one more level of precision than minimum/maximum
- SD/SEM: in one more level of precision than Mean/median
- n will be presented as an integer
- CV% will be presented to the nearest tenth

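### The SAP pre-specifies no dose-minus-placebo estimate or interval for any outcome, and for URR, Kt/V, BUN, potassium and clotting it omits the protocol's change from baseline without declaring it.

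*SAP*

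**What the plan says.** Protocol 9.2 sets the dialysis-efficiency endpoint as "total dialysate urea (single pool Kt/V and URR) after xisomab 3G3-treatment versus pre-treatment and placebo", and words the potency endpoint (coagulation, thrombus and protein accumulation) against the same two comparators. Protocol 14.3.3 plans a change from baseline in the PD endpoints, summarized descriptively by treatment. It takes as baseline any predose value from Day -7 to Day 1, with no rule for choosing or averaging. It also states: "Placebo patients from Cohort 1 and Cohort 2 will be pooled for analysis". For access-site bleeding, Protocol 14.3.1 says: "Treatment versus pre-treatment, placebo, and post-treatment results will be compared".

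The SAP plans the following:

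- **URR and Kt/V (7.2.3):** "URR and Kt/V values will be listed and summarized by treatment and Day in Tables for all subjects in the Safety Population". The text lists Days -7, -5, 1, 3, 5 and 12; the shells also show Day -3.
- **BUN and potassium (7.2.2):** the change is pre-dialysis minus post-dialysis within one session, not a change from run-in.
- **Clotting (7.2.4):** category counts by arm and day.
- **Bleeding time (8.10):** summary statistics by arm and time point.
- **aPTT (7.2.1):** "aPTT values will be listed and summarized by treatment and time points in Tables and Figures". Postdose values are also divided by the mean of the pre-dialysis values on Days -7, -5, -3 and 1.
- **Laboratory tests, vital signs and ECG (8.4 to 8.6):** change from baseline by arm.

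No table, figure or shell shows a between-arm difference or a confidence interval. SAP 9 lists one departure from the protocol, the length of dialysis, and otherwise declares the two documents aligned.

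**The concern.** The placebo arm and the heparin-free inpatient run-in are justified in Protocol 8.4.1 by the comparison they make possible. Each patient gives three run-in sessions on the same measures as the treated sessions. For the dialysis-efficiency and clotting outcomes these sessions are tabulated and then not used. In-text Tables 11-3 to 11-6 print arithmetic means without spread, so the reader compares bare means from 6 to 8 patients per arm by eye. Any dose-placebo contrast reported later would be chosen after the data are seen.

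**Working it through.** **1. Arm sizes.** Protocol 14.1 gives "9-12 per cohort with a ratio of 2:1 of active study drug:placebo". A cohort of 12 has 8 active and 4 placebo; a cohort of 9 has 6 and 3. Pooling placebo over two cohorts gives 8/8/8 (total 24) or 6/6/6 (total 18), which agrees with the stated maximum of 24. No alpha, power, SD or effect size is stated, so there is no power figure to reproduce.

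**2. Protocol against SAP on change from baseline.** Protocol 14.3.3 covers aPTT, BUN, potassium, thrombus accumulation, dialysate urea, URR and Kt/V. SAP 7.2 keeps a baseline comparison for aPTT only. BUN and potassium also appear as serum chemistry, so SAP 8.4 gives their single values a change from baseline at the safety time points, but not the amount removed per session.

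**3. Precision of one dose minus pooled placebo, in SD units.** Assumptions: equal variance in the three arms, the same correlation ρ between any two sessions, one post-dose session analysed, and k run-in sessions averaged.

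- Unadjusted half-width = t(0.975; 3n−3) × √(2/n). For n = 8: 2.080 × 0.500 = 1.04. For n = 6: 2.131 × 0.577 = 1.23.
- Adjusted half-width = t(0.975; 3n−4) × √(2/n) × √V, with V = 1 − kρ²/(1 + (k−1)ρ).
- Example, k = 3, ρ = 0.7: V = 1 − 1.47/2.4 = 0.388. For n = 8: 2.086 × 0.500 × 0.622 = 0.65.
- Equivalent sample-size factor = 1/V.

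| ρ (assumed) | V, k = 3 | Half-width, n = 8 | Half-width, n = 6 | 1/V, k = 3 | 1/V, k = 2 |
|---|---|---|---|---|---|
| unadjusted | 1 | 1.04 | 1.23 | 1 | 1 |
| 0.3 | 0.831 | 0.95 | 1.13 | 1.2 | 1.2 |
| 0.5 | 0.625 | 0.82 | 0.98 | 1.6 | 1.5 |
| 0.7 | 0.388 | 0.65 | 0.77 | 2.6 | 2.4 |
| 0.8 | 0.262 | 0.53 | 0.63 | 3.8 | 3.5 |

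The k = 2 column applies if only Days -7 and -5 are used, as the text of SAP 7.2.3 reads. With variance from the two compared arms only (2n−2 degrees of freedom), the unadjusted half-widths are 1.07 and 1.29.

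**4. Change score or covariate.** For a plain change from the run-in mean, V = 1 + (1 + (k−1)ρ)/k − 2ρ. At ρ = 0.3 this is 0.933 for k = 3 and 1.05 for k = 2, so with two sessions it is worse than no adjustment. At ρ = 0.7 and k = 3 it is 0.400, close to the 0.388 from covariate adjustment. Using the run-in mean as a covariate is safer when ρ is unknown.

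**5. Items to settle before any contrast.**

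- *Kt/V formula (SAP 7.2.3).* With illustrative R = 0.30, t = 4 h and UF/Wt = 0.03: ln(0.30 − 0.032) + (4 − 1.05) × 0.03 = −1.317 + 0.089 = −1.23. With R multiplied by 100, as in the Table 11-5 footnote: ln(29.968) + (4 − 105) × 0.03 = 3.40 − 3.03 = 0.37. Inclusion criterion 1 asks for at least 1.2. The text, the footnotes and the criterion must be reconciled.
- *Placebo aPTT.* A shell note in SAP 11.3 removes summary statistics from Tables 14.2.5.1.3 and 14.2.5.1.6, while SAP 7.2.1 promises them for pooled placebo. SAP 6.6 has such a rule for placebo drug concentrations, so this may be a table-number slip.

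**The case against.** The protocol promises description, not inference, and says so: "The sample size chosen for this study was selected without statistical considerations". The Section 14 shells for BUN, potassium, Kt/V and aPTT give individual values with n, mean, SD and SEM, so an unadjusted difference and interval can be computed from them, and an adjusted one from the individual values. This stands. A reader might infer that the secondary endpoints cannot be answered at all; the documents do not support that. What is missing is pre-specification.

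Three other strong readings also fail:

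- That no outcome is adjusted for baseline: aPTT uses a four-value predose mean, and laboratory tests, vital signs and ECG have change from baseline. These are changes within an arm, not contrasts with placebo.
- That the protocol's promise to compare results (14.3.1) covers the PD endpoints: that sentence concerns access-site bleeding only. The PD wording is in 9.2 and 14.3.3.
- That the SAP forbids further analysis: unlisted exploratory analyses "will be considered out of scope and must be described in the CSR", so they are foreseen, and Protocol 14.3.3 allows additions after data review. Neither route fixes the contrast beforehand.

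The remedy also has limits. Five outcomes, two doses and four post-dose days (1, 3, 5, 12) give 5 × 2 × 4 = 40 intervals from 18 to 24 patients, and BUN removal, URR and Kt/V all come from the same pair of BUN values. Cohorts run in sequence, so half of the pooled placebo (4 of 8, or 3 of 6) is not concurrent with a given dose. Equal variance is doubtful for aPTT, which is one reason to use its logarithm. These limits call for labelling and display by cohort; they do not favour bare means.

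**Conclusion.** The point holds in this form: no dose-minus-placebo estimate or interval is pre-specified for any outcome. For URR, Kt/V, BUN removal, potassium removal and clotting, the protocol's change from baseline is also dropped while SAP 9 declares alignment. This is an inexpensive improvement to the analysis plan, not a flaw that invalidates the trial.

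The gain depends on a correlation that the documents do not give. A reader might take the factor of 2.6 at ρ = 0.7 as the size of the loss; the defensible statement is a range from about 1.2 (ρ = 0.3) to 3.8 (ρ = 0.8), under equal variances and three run-in sessions. The figures describe a single-session analysis, not a full repeated-measures model. Even after adjustment, half-widths stay between about 0.53 and 1.13 SD, so the result should be read as estimation and not as a test.

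**What to change.** In SAP 7.2:

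1. For URR, Kt/V, BUN removal, potassium removal and log aPTT, add each dose minus pooled placebo with a 95% CI, adjusted for the patient's run-in mean (Days -7, -5 and -3). Use ANCOVA by session or a simple repeated-measures model. Label it descriptive and report no p-values.
2. Add Day -3 to the text of 7.2.3, and define the run-in mean as the baseline, since Protocol 14.3.3 gives no averaging rule.
3. For clotting, report the change in grade from run-in by arm, and a between-arm difference with an exact or rank-based interval that keeps the ordinal scale. Add the Day -3 row missing from Table 11-8.
4. State that about half of the pooled placebo is non-concurrent with each dose, and show results by cohort as well.
5. Before any contrast, reconcile the Kt/V formula and the placebo aPTT shell note.
6. If the change from baseline is deliberately left out for some endpoints, declare it in SAP 9.

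The cost is SAP text and about one table per endpoint, settled before unblinding, with no new data or procedures. The drawback is wide intervals from a small-sample model that assumes similar variances across arms; the text should say so.
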